11.1.7. Protocol Amendments

No change or amendment to this protocol may be made by the investigator or the Sponsor after the protocol has been agreed to and signed by all parties unless such change(s) or amendment(s) has (have) been agreed upon by the investigator or the Sponsor. Any change agreed upon will be recorded in writing, and the written amendment will be signed by the investigator and the Sponsor. Institutional review board approval is required prior to the implementation of an amendment, unless overriding safety reasons warrant immediate action, in which case the IRB(s)/IEC(s) will be promptly notified.

Any modifications to the protocol or the ICF, which may impact the conduct of the study, potential benefit of the study, or may affect participant safety, including changes of study objectives, study design, participant population, sample sizes, study procedures, or significant administrative aspects will require a formal amendment to the protocol. Such amendment will be released by the Sponsor, agreed by the investigator(s), and approved by the relevant IRB(s)/IEC(s) prior to implementation. A signed and dated statement that the protocol, any subsequent relevant amended documents and the ICF have been approved by relevant IRB(s)/IEC(s) must be provided to the Sponsor before the study is initiated.

Administrative changes of the protocol are minor corrections and/or clarifications that have no effect on the way the study is to be conducted. These administrative changes will be released by the Sponsor, agreed by the investigator(s), and notified to the IRB(s)/IEC(s).

11.1.8. Protocol Violations and Deviations

The investigator or designee must document and explain in the participant's source documentation any deviation from the approved protocol. The investigator may implement a deviation from, or a change to, the protocol to eliminate an immediate hazard to study participants without prior IRB approval. As soon as possible after such an occurrence, the implemented deviation or change, the reasons for it, and any proposed protocol amendments should be submitted to the IRB for review and approval, to the Sponsor for agreement, and to the regulatory authorities, if required.

A deviation from the protocol is an unintended or unanticipated departure from the procedures or processes approved by the Sponsor and the IRB and agreed to by the investigator. Deviations usually have an impact on individual participants or a small group of participants and do not

involve inclusion/exclusion or primary endpoint criteria. A protocol violation occurs when the participant or investigator does not adhere to the protocol, resulting in a significant additional risk to the participant. Protocol violations can include nonadherence to inclusion or exclusion criteria, enrollment of the participant without prior Sponsor approval, or nonadherence to FDA regulations or ICH E6(R2) guidelines.

Protocol violations and deviations will be documented by the clinical monitor throughout the course of monitoring visits. The investigator will be notified in writing by the monitor of violations and deviations. The IRB should be notified of all protocol violations and deviations, if appropriate, in a timely manner.

11.1.9. Data Protection

Participants will be assigned a unique identifier by the Sponsor. Any participant records or datasets that are transferred to the Sponsor will contain the identifier only; participant names or any information which would make the participant identifiable will not be transferred.

The participant must be informed that his/her personal study-related data will be used by the Sponsor in accordance with local data protection law. The level of disclosure must also be explained to the participant.

The participant must be informed that his/her medical records may be examined by Clinical Quality Assurance auditors or other authorized personnel appointed by the Sponsor, by appropriate IRB/IEC members, and by inspectors from regulatory authorities.

Individual participant medical information obtained as a result of this study is considered confidential, and disclosure to third parties is prohibited. Information will be accessible to authorized parties or personnel only. Medical information may be given to the participant's physician or to other appropriate medical personnel responsible for the participant's well-being. Each participant will be asked to complete a form allowing the investigator to notify the participant's primary healthcare provider of his/her participation in this study.

All laboratory specimens, evaluation forms, reports, and other records will be identified in a manner designed to maintain participant confidentiality. All records will be kept in a secure storage area with limited access. Clinical information will not be released without the written permission of the participant, except as necessary for monitoring and auditing by the Sponsor, its designee, relevant regulatory authority, or the IRB.

The investigator and all employees and coworkers involved with this study may not disclose or use for any purpose other than performance of the study, any data, record, or other unpublished, confidential information disclosed to those individuals for the purpose of the study. Prior written

agreement from the Sponsor or its designee must be obtained for the disclosure of any confidential information to other parties.

11.1.10. Sample Retention and Future Biomedical Research

Samples may be used for purposes related to ZIKV research, in particular assay development, assay validation, and animal challenge studies. There will be no human genetic testing (whole genome sequencing or creation of cell lines) performed on these samples. The DNA of the CMI subset participants may be used to further characterize the immune response to mRNA-1893 vaccine, but only epitopes relevant to the ZIKV-specific immune response will be investigated. The samples may be stored for 20 years or until the study team has determined that specimens are no longer needed, per local requirements. In addition, identifiable samples can be destroyed at any time at the request of the participant.

11.1.11. Study Safety Oversight by Oversight Safety Team and Data Safety Monitoring Board

Study safety will be monitored by an OST that will include the investigators participating in the study and the protocol team, which will include the CRO Medical Monitor and the Sponsor Clinical Development Physician and may include additional representatives from the Sponsor Project Team. The CRO Medical Monitor will be responsible for performing a review of the enrollment and study-related safety data with oversight by the Sponsor Clinical Development Physician. During the Vaccination Period, a formal biweekly meeting/teleconference will be scheduled among the CRO Medical Monitor, the Sponsor Clinical Development Physician, and the Lead Investigator (or alternate investigator) to review safety events in a blinded fashion. Once all participants in all treatment arms enter the Follow-Up Period, the interval of these meetings may be extended to monthly. This decision will be confirmed by the protocol team.

In addition, an independent DSMB will be established for Study mRNA-1893-P201. It will be composed of experts with experience in clinical development and vaccines and with expertise in flaviviruses. Members of the DSMB will be independent from the study conduct and free of conflict of interest. The DSMB will convene on an approximately quarterly basis until study end. Additionally, the DSMB may convene at any time if there is an ad-hoc safety concern detected by the protocol team. This independent board will be informed of the progress and conduct of the study; their primary responsibility will be to review unblinded study data to evaluate the safety findings. All AEs, SAEs, AESIs, and MAAEs will be reviewed by the board, and they will be asked to provide recommendations and guidance as to management of safety follow-up within the study. In addition, should immunogenicity findings request further opinion, the DSMB would be asked to review unblinded available immunogenicity data and provide guidance.

Details regarding the composition, responsibilities, and procedures of the OST and the DSMB will be presented in the OST and DSMB charters, respectively.

11.1.12. Dissemination of Clinical Study Data

The Sponsor shares information about clinical studies and results on publicly accessible websites, based on international and local legal and regulatory requirements, and other clinical study disclosure commitments established by pharmaceutical industry associations. These websites include clinicaltrials.gov, European Union clinical trial register (eu.ctr), etc., as well as some national registries.

ModernaTX, Inc.
Protocol: mRNA-1893-P201, Amendment 3

In addition, results from clinical studies are required to be submitted to peer-reviewed journals following internal company review for accuracy, fair balance, and intellectual property. For those journals that request sharing of the analyzable data sets that are reported in the publication, interested researchers are directed to submit their request to clinical study data request.com.

09 Dec 2021

mRNA-1893

Individual participant data and supporting clinical documents are available for request at clinical study data request.com. While making information available the privacy of participants in clinical studies sponsored by the Sponsor is assured. Details on data sharing criteria and process for requesting access can be found at this web address: clinical study data request.com.

11.1.13. Data Quality Assurance and Quality Control

Data collection is the responsibility of the clinical study staff at the site under the supervision of the site investigator. The investigator is responsible for ensuring the accuracy, completeness, legibility, and timeliness of the data reported.

- All participant data relating to the study will be recorded in the eCRF unless transmitted to
 the Sponsor or designee electronically (eg, laboratory data). The investigator is responsible
 for verifying that data entries are accurate and correct by physically or electronically
 signing the eCRF.
- The investigator must maintain accurate documentation (source data) that supports the information entered in the eCRF.
- The investigator must permit study-related monitoring, audits, IRB/IEC review, and regulatory agency inspections and provide direct access to source data documents.
- Monitoring details describing strategy (eg, risk-based initiatives in operations and quality such as Risk Management and Mitigation Strategies and Analytical Risk-Based Monitoring), methods, responsibilities and requirements, including handling of noncompliance issues and monitoring techniques (central, remote, or on-site monitoring) are provided in the Monitoring Plan.
- The Sponsor or designee is responsible for the data management of this study including quality checking of the data.
- The Sponsor assumes accountability for actions delegated to other individuals (eg, CROs).
- Study monitors will perform ongoing source data verification to confirm that data entered into the eCRF by authorized site personnel are accurate, complete, and verifiable from source documents; that the safety and rights of participants are being protected; and that

the study is being conducted in accordance with the currently approved protocol and any other study agreements, ICH GCP, and all applicable regulatory requirements.

Records and documents, including signed ICFs, pertaining to the conduct of this study must
be retained by the investigator for 2 years after study completion unless local regulations
or institutional policies require a longer retention period. No records may be destroyed
during the retention period without the written approval of the Sponsor. No records may
be transferred to another location or party without written notification to the Sponsor.

Quality assurance (QA) includes all the planned and systematic actions that are established to ensure that the clinical study is performed and the data are generated, documented (recorded), and reported according to ICH GCP and local/regional regulatory standards.

A QA representative from the Sponsor or its qualified designee, who is independent of and separated from routine monitoring, may periodically arrange inspections/audits of the clinical study by reviewing the data obtained and procedural aspects. These inspections may include on-site inspections/audits and source data checks. Direct access to source documents is required for the purpose of these periodic inspections/audits.

11.1.14. Data Collection and Management

This study will be conducted in compliance with the ICH document "Guidance for Industry-E6 (R2) Good Clinical Practice: Consolidated Guidance," dated November 2016. This study will also be conducted in accordance with the most recent version of the Declaration of Helsinki.

This study will use electronic data collection to collect data directly from the investigational site using eCRFs. The investigator is responsible for ensuring that all sections of each eCRF are completed promptly and correctly and that entries can be verified against any source data.

Study monitors will perform source document verification to identify inconsistencies between the eCRFs and source documents. Discrepancies will be resolved in accordance with the principles of GCP. Detailed study monitoring procedures are provided in the Clinical Monitoring Plan.

Adverse events will be coded according to the Medical Dictionary for Regulatory Activities. Concomitant medications will be coded using the WHO – Drug Reference List.

11.1.15. Source Documents

Source documents are original documents or certified copies, and include, but are not limited to, diary cards, medical and hospital records, screening logs, ICFs, telephone contact logs, and worksheets. Source documents provide evidence for the existence of the participant and substantiate the integrity of the data collected. Source documents are filed at the investigator's site.

Protocol: mRNA-1893-P201, Amendment 3

Data reported on the paper case report form or entered into the eCRF that are transcribed from source documents must be consistent with the source documents or the discrepancies must be explained. The investigator may need to request previous medical records or transfer records, depending on the study. Also, current medical records must be available.

The Sponsor or its designee requires that the investigator prepare and maintain adequate and accurate records for each participant treated with the IP. Source documents such as any hospital, clinic, or office charts and the signed ICFs are to be included in the investigator's files with the participant's study records.

11.1.16. **Retention of Records**

The Principal Investigator must maintain all documentation relating to the study for a period of at least 2 years after the last marketing application approval or, if not approved, 2 years following the discontinuance of the test article for investigation.] If this requirement differs from any local regulations, the local regulations will take precedence unless the local retention policy is less than 2 years.

If it becomes necessary for the Sponsor or the regulatory authority to review any documentation relating to the study, the investigator must permit access to such records. No records will be destroyed without the written consent of the Sponsor, if applicable. It is the responsibility of the Sponsor to inform the investigator when these documents no longer need to be retained.

11.1.17. **Study and Site Closure**

If the study is prematurely terminated or suspended, the Sponsor shall promptly inform the investigators, the IECs/IRBs, the regulatory authorities, and any CRO(s) used in the study of the reason for termination or suspension, as specified by the applicable regulatory requirements. The investigator shall promptly inform the participant and should assure appropriate participant therapy and/or follow-up.

The Sponsor or designee reserves the right to close the study site or terminate the study at any time for any reason at the sole discretion of the Sponsor.

The investigator may initiate study site closure at any time, provided there is reasonable cause and sufficient notice is given in advance of the intended termination.

Reasons for the early closure of a study site by the Sponsor or investigator may include but are not limited to:

• Continuation of the study represents a significant medical risk to participants.

- Failure of the investigator to comply with the protocol, the requirements of the IRB/IEC or local health authorities, the Sponsor's procedures, or GCP guidelines.
- Inadequate recruitment of participants by the investigator.
- Discontinuation of further mRNA-1893 development.

Study sites will be closed upon study completion. A study site is considered closed when all required documents and study supplies have been collected and a study site closure visit has been performed.

11.1.18. Publication Policy

The results of this study may be published or presented at scientific meetings. If this is foreseen, the investigator agrees to submit all manuscripts or abstracts to the Sponsor before submission. This allows the Sponsor to protect proprietary information and to provide comments.

The Sponsor will comply with the requirements for publication of study results. In accordance with standard editorial and ethical practice, the Sponsor will generally support publication of multicenter studies only in their entirety and not as individual site data. In this case, a coordinating investigator will be designated by mutual agreement.

Authorship will be determined by mutual agreement and in line with International Committee of Medical Journal Editors authorship requirements.

The clinical study plan and the results of the study will be published on www.ClinicalTrials.gov in accordance with 21 CFR 50.25(c). The results of and data from this study belong to the Sponsor.

11.2. APPENDIX 2: Adverse Events: Definitions and Procedures for Recording, Evaluating, Follow-Up, and Reporting

11.2.1. Definition of an AE

AE Definition

- An AE is any untoward medical occurrence associated with the use of a drug in humans, regardless of whether it is considered drug related.
- A treatment-emergent AE is defined as any event not present before exposure to the IP or any event already present that worsens in intensity or frequency after exposure to the IP.

An AR is any AE for which there is a reasonable possibility that the IP caused the AE (Section 11.2.3). For the purposes of investigational new drug safety reporting, "reasonable possibility" means that there is evidence to suggest a causal relationship between the IP and the AE.

An unsolicited AE is any AE reported by the participant that is not specified as a solicited AR in the protocol or is specified as a solicited AR in the protocol but starts outside the protocol-defined post-injection period for reporting solicited ARs (ie, for the 7 days after each IP injection).

Events Meeting the AE Definition

- Exacerbation of a chronic or intermittent pre-existing condition including either an increase in frequency and/or intensity of the condition.
- New conditions detected or diagnosed after the first dose of IP even though they may have been present before the start of the study.

Events NOT Meeting the AE Definition

- Medical or surgical procedure (eg, endoscopy, appendectomy): the condition that leads to the procedure should be the AE.
- Situations in which an untoward medical occurrence did not occur (social and/or convenience admission to a hospital).

11.2.2. Definition of an SAE

If an event is not an AE per definition above, then it cannot be an SAE even if serious conditions are met (eg, hospitalization for signs/symptoms of the disease under study, death due to progression of disease).

An AE is considered "serious" if, in the view of either the investigator or the Sponsor, it results in any of the following outcomes (21 CFR 312.32(a)):

An SAE is defined as any untoward medical occurrence that, at any dose:

a. Results in death

A death that occurs during the study or that comes to the attention of the investigator during the protocol-defined follow-up period must be reported to the Sponsor, regardless of whether it is considered IP related.

b. Is life-threatening

An AE is considered life-threatening if, in the view of either the investigator or the Sponsor, its occurrence places the participant at immediate risk of death. It does not include an AE that might have caused death if it had occurred in a more severe form.

c. Requires inpatient hospitalization or prolongation of existing hospitalization

In general, hospitalization indicates that the participant was admitted to the hospital or emergency ward for at least one overnight stay for observation and/or treatment that would not have been appropriate in the physician's office or outpatient setting. The hospital or emergency ward admission should be considered an SAE regardless of whether opinions differ as to the necessity of the admission. Complications that occur during hospitalization will be recorded as AEs; however, if a complication/AE prolongs hospitalization or otherwise fulfills the SAE criteria, the complication/AE will be recorded as a separate SAE.

d. Results in significant incapacity disability/incapacity

- The term disability means a substantial disruption of a person's ability to conduct normal life functions.
- This definition is not intended to include experiences of relatively minor medical significance such as uncomplicated headache, nausea, vomiting, diarrhea, influenza, and accidental trauma (eg, sprained ankle) that may interfere with or prevent everyday life functions but do not constitute a substantial disruption.

e. Is a congenital anomaly/birth defect

f. Is a medically important event:

• Medical judgment should be exercised in deciding whether SAE reporting is appropriate in other situations such as important medical events that may not be immediately life-threatening or result in death or hospitalization but may jeopardize the participant or may require medical or surgical intervention to prevent one of the other outcomes listed in the above definition. These events should usually be considered serious.

Examples of such events include allergic bronchospasm requiring intensive treatment in an emergency room or at home, blood dyscrasias or convulsions that do not result in hospitalization, or development of drug dependency or drug abuse.

If an event meets any of the above definitions, regardless of the severity or relationship of the event to the study product, the event must be reported to the Sponsor as described in Section 8.6.

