There is a theoretical risk that active vaccination to prevent novel viral infection may cause a paradoxical increase in the risk of disease. This possibility is based on the rare phenomenon of vaccine-associated disease enhancement, which was first seen in the 1960s with 2 vaccines made in the same way (formalin-inactivated whole virus) and designed to protect children against infection with respiratory syncytial virus (Chin et al 1969) or measles (Fulginiti et al 1967). Antibody disease enhancement has also been proposed as a possible explanation for the cases of more serious disease associated with dengue vaccination (Thomas and Yoon 2019; WHO 2018); this phenomenon was already known in cases of a dengue reinfection caused by a heterologous serotype. It is not known if mRNA-1893 will increase the risk of ZIKV-enhanced disease and also the risk of dengue-virus-enhanced disease because of the close relationship between dengue virus and ZIKV (flavivirus family, geographic location, cross-reactivity). To monitor this risk, the Sponsor will perform a careful safety follow-up throughout the entire study duration by establishing an Oversight Safety Team (OST) and an independent Data Safety Monitoring Board (DSMB). The OST will perform a biweekly review of safety events in a blinded fashion. In addition, the DSMB will convene on an approximately quarterly basis until study end and at any time if there is an ad-hoc safety concern detected by the OST. The DSMB will review unblinded study data to evaluate the safety findings. All AEs, SAEs, and medically attended AEs (MAAEs) will be reviewed in terms of frequency and severity by the board and they will be asked to provide recommendations and guidance as to management of safety follow-up within the study (Section 11.1.1)

There have been very rare reports of myocarditis and pericarditis occurring after vaccination with COVID-19 mRNA vaccines. The majority of the cases have been reported in young males shortly after the second dose of the vaccine. The risk is highest in males under the age of 40 years, specifically males between 12 through 17 years. Symptoms include chest pain, shortness of breath, or palpitations. Study participants should seek medical attention and also notify study site staff if

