4.1.2. Vaccination Period

All participants will receive IP injections at Visit 1 (Day 1) and Visit 3 (Day 29). Participants will be asked to complete an electronic diary (eDiary) to monitor solicited ARs for 6 days after each IP injection (Days 1 through 7 and Days 29 through 35) and to monitor unsolicited AEs for 28 days after each IP injection (Days 1 through 57). Serious AEs, AESIs and MAAEs will be monitored from Day 1 for approximately 6 months (Visit 10 [Day 196]) after the last IP injection.

Blood samples will be collected from all participants at Days 1 (baseline), 8, 29, 36, 57, 85, and 196 for the assessment of antibody-mediated immunogenicity. Blood samples will be collected from a subset of participants (cell-mediated immunity [CMI] subset) at Days 1 (baseline), 29, 36, 57, and 196 for peripheral blood mononuclear cell (PBMC) collection and assessment of cellular immunity. Blood samples collected from all participants at Days 85 and 196 will be used for detection of asymptomatic flavivirus infections.

In case of signs or symptoms suggesting a flavivirus infection (mostly dengue and Zika in the areas where the study will be performed), an additional blood sample will be collected to confirm the diagnosis via specific serology and reverse transcriptase polymerase chain reaction (RT-PCR), and clinical information will be carefully collected to evaluate the severity of the clinical case. Those symptoms are not specific; however, an association of acute fever onset with maculopapular rash, arthralgia, and conjunctivitis during the seasonal circulation of mosquitos must trigger samplings. Also, special attention will be paid to the reporting of neurological signs or symptoms evoking Guillain-Barré syndrome.

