8.2. Clinical Laboratory Assessments

8.2.1. Baseline and Safety Laboratory Assessments

There are no screening criteria based on the flavivirus serostatus, meaning all participants are enrolled regardless of serostatus. However, this baseline flavivirus status will be confirmed by serology testings (dengue IgG and IgM, West Nile IgG and IgM) performed on a blood sample collected prior to administration of the first vaccination in order to eventually ensure that an approximate equal distribution of participants among subgroups is respected for the statistical analysis.

A point-of-care urine pregnancy test will be performed at the Eligibility Visit and before each IP injection (or at any time at the discretion of the investigator) for all female participants of childbearing potential.

The FSH level may be measured at the discretion of the investigator to confirm menopausal status.

There are no screening safety laboratory tests at the time of the eligibility evaluation of the participant. However, additional tests may be performed for safety reasons at any time during the study if determined necessary by the investigator or required by local regulations. Specifically, if the participant presents with signs or symptoms evoking a flavivirus infection, standard-of-care tests and treatment will apply, and results will be reported in the source documents and in the AE section of the eCRF.

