11.2.13. Adverse Events of Special Interest Terms

Investigators should report all events that fall into the categories presented in Table 15 as an AESI per the reporting processes in Section 11.2.12. These AESIs are medical concepts that are generally of interest in vaccine safety surveillance as per the Brighton Collaboration and Safety Platform for Emergency Vaccines.

Table 15: Adverse Events of Special Interest

Medical Concept	Additional Notes
Thrombocytopenia	 Platelet counts < 150 × 10⁹ Including but not limited to immune thrombocytopenia, platelet production decreased, thrombocytopenia, thrombocytopenic purpura, thrombotic thrombocytopenic purpura, or hemolysis, elevated liver enzymes, and low platelet count (HELLP) syndrome
New onset of or worsening of the following neurologic diseases:	 Guillain-Barré Syndrome Acute disseminated encephalomyelitis (ADEM) Idiopathic peripheral facial nerve palsy (Bell's palsy) Seizures including but not limited to febrile seizures and/or generalized seizures/convulsions

Medical Concept	Additional Notes	
Anaphylaxis	 Anaphylaxis as defined per Section 11.2.13.2 Follow reporting procedures in Section 11.2.12 	
Myocarditis/Pericarditis	 Myocarditis Pericarditis Myopericarditis Refer to Section 11.2.13.1 for details. 	

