6.5. Analysis of occurrence of Flavivirus Infection

Analyses of flavivirus infection will be performed using the FAS. The number and percentage of subjects with at least one positive flavivirus result (Dengue PCR, ZIKV PCR) post-baseline and occurring at any time during the study duration will be provided by baseline flavivirus serostatus and treatment arm. Subjects with at least one positive flavivirus result at post-baseline will be presented in a listing.

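### The SAE definition's disease-under-study example contradicts the AE definition it relies on, and SAP 6.5 has no severity summary of flavivirus cases

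*Protocol*

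**What the plan says.** **The risk.** Protocol 2.3.2 (Anticipated Risks) states: "It is not known if mRNA-1893 will increase the risk of ZIKV-enhanced disease and also the risk of dengue-virus-enhanced disease". It then describes how this will be monitored: regular blinded review by the oversight safety team, and roughly quarterly unblinded DSMB review of AEs, SAEs and MAAEs by frequency and severity. SAEs and MAAEs over the whole study are primary safety endpoints (Protocol 3.1, Table 3).

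**The SAE definition.** Protocol 11.2.2 opens with a conditional rule, limited to events that are not AEs under the preceding definition. Of such an event it says that "it cannot be an SAE even if serious conditions are met (eg, hospitalization for signs/symptoms of the disease under study". In full, the examples in brackets are "hospitalization for signs/symptoms of the disease under study, death due to progression of disease".

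**Recording of flavivirus illness.** For a participant with signs suggesting flavivirus infection, Protocol 8.2.1 says that "results will be reported in the source documents and in the AE section of the eCRF". Protocol 4.1.2 adds that "clinical information will be carefully collected to evaluate the severity of the clinical case", and 4.1.3 repeats this for the Extension Period.

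**The analysis.** SAP 6.5 plans, in the FAS, "The number and percentage of subjects with at least one positive flavivirus result (Dengue PCR, ZIKV PCR) post-baseline", by baseline serostatus and treatment arm, plus a listing of positive participants. It does not mention severity.

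**The concern.** Enhanced disease would show as infections that are more severe: admissions, deaths, and higher severity grades among those infected. Two parts of the plan sit badly with that.

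First, the bracketed examples in 11.2.2 look like wording from a treatment trial, where participants enter with the disease and its progression is an efficacy outcome. Here, Zika illness after injection is a new event, and a severe one is what the risk section asks the study to watch for. A site that takes the examples at face value has a printed reason not to file a Zika admission as an SAE.

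Second, severity information is to be gathered on every suspected case, but the one analysis devoted to flavivirus infection does not use it. If a vaccine arm had fewer infections and a larger share of them were severe, the SAP 6.5 count would show only the reduction.

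**Working it through.** No design calculation bears on this point, so the check sets the passages side by side.

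**1. Does the condition in 11.2.2 catch Zika illness?** The rule covers only events that are not AEs under the preceding definition. Protocol 11.2.1 defines an AE broadly, whether or not it is related to the product, and counts conditions first found after the first dose. It lists two kinds of non-AE: a procedure (as opposed to the condition behind it), and situations with no untoward occurrence, such as a social admission. Zika illness is neither. The condition is not met, yet the examples present it as met.

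**2. Do the other rules agree with the examples?**

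| Place | What it implies for a Zika admission or death |
|---|---|
| Protocol 11.2.2, bracketed examples | Offered as an event that cannot be an SAE |
| Protocol 11.2.1 | An AE |
| Protocol 8.2.1 | Recorded in the AE section of the eCRF |
| Protocol 11.2.2, item a | A death is reported whatever its cause |
| Protocol 11.2.2, item c | An admission is an SAE even if its need is disputed |
| Protocol 11.2.11 | An AE meeting SAE criteria reaches the sponsor within 24 hours |

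Five entries point one way and one the other.

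**3. If a site misreads the example, where does the case go?** Symptomatic sampling takes place at an unscheduled visit (Protocol Table 1). Unscheduled site visits fall under the MAAE definition (11.2.4), and MAAEs are collected to Day 700 (8.5). The case would still be captured, but 11.2.4 sets no 24-hour limit, and the case would be missing from the SAE tables.

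**4. Which severity summaries exist?** SAP 6.3.1 summarizes unsolicited AEs by serostatus, vaccination group and stage, including an overall stage that runs to study end. SAP 6.3.1.1 and 6.3.1.2 cover serious, fatal, severe and medically attended TEAEs. SAP 6.3.1.4 tabulates TEAEs by system organ class, preferred term and maximum severity. These are by-arm severity tables, but they are built on preferred terms. They do not link severity to a positive test, and one illness coded under several terms can be split.

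**5. Scale.** Protocol Table 7 plans 3 × 200 = 600 vaccinees, of whom 3 × 100 = 300 are seropositive, with 100 per arm-by-serostatus cell. Protocol Table 11 gives 1 event in 100 as 1.00% (95% CI 0.03% to 5.45%). Recomputing the Clopper-Pearson upper limit as the 0.975 quantile of Beta(2, 99) gives 5.446%, which agrees. If that single event were misfiled, the cell would read 0/100, with upper limit 1 − 0.025^(1/100) = 3.62%. One case is therefore the whole recorded signal in a cell. This is an illustration only, since the documents give no expected number of cases.

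**The case against.** The strongest reply is that the rule is conditional. Read to the letter, 11.2.2 sends the site back to 11.2.1, where Zika illness is an AE, and items a and c then make the death or admission an SAE with 24-hour reporting. That is correct. The defect is a contradiction that invites misreading. It is not an operative exclusion. What survives is that an example tells the reader which events meet the condition, and these examples tell the reader the wrong thing.

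A reader might go further and infer that severe cases escape expedited reporting and any comparison of severity by arm. The documents do not support this. Expedited reporting fails only on the misreading. By-arm TEAE severity tables are planned, and section 2.3.2 provides unblinded DSMB review of severity for this very risk. Nor do the examples plainly reach dengue, because the disease under study is most naturally Zika.

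A reader might also fault Table 15 for not listing dengue or Zika illness as an AESI. The omission is real, but section 11.2.13 bases the list on general vaccine-surveillance concepts, and it already includes Guillain-Barré syndrome and thrombocytopenia. Adding flavivirus illness is a preference and does not correct an error.

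On the analysis, it is fair to say that cases may be few, that there is no hypothesis testing, and that every positive participant is listed. It is also true that severe cases per confirmed case is not a randomized comparison, because infection occurs after randomization and the vaccine may change who is infected. These points limit what a table can show. They do not explain why severity that is collected for a named risk has no summary of its own.

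**Conclusion.** The point holds as two limited defects. The bracketed examples in Protocol 11.2.2 contradict 11.2.1, 8.2.1 and items a and c of 11.2.2 itself, and a site could misread them and leave a hospitalized Zika case out of the primary SAE endpoint. SAP 6.5 has no flavivirus-specific severity summary, although the protocol collects the information and names enhanced disease as a risk. The first defect concerns Zika; the second covers Zika and dengue.

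The size cannot be put as a rate, because it depends on how many cases occur and whether any site misreads the example, and the documents give neither. If cases are few, which is an assumption, each misfiled severe case carries weight. The conclusion rests on reading the disease under study as Zika and on the general TEAE tables being the only other planned by-arm severity summaries. Both changes are worth making because they are specific and nearly free. The finding does not show that severe cases would go unreported.

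**What to change.** 1. **Protocol 11.2.2:** delete the bracketed examples and reconcile the opening sentence with 11.2.1, 8.2.1 and items a and c of 11.2.2, so that sites have one instruction for a Zika admission or death.
2. **SAP 6.5:** add a descriptive table of participants with flavivirus infection by the severity already collected (hospitalized or SAE, fatal, maximum AE severity), by treatment arm and baseline serostatus. Use all participants in the arm as the denominator, which keeps the randomized comparison. If a proportion per confirmed case is also shown, label it descriptive, because it conditions on an outcome that arises after randomization.

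The cost is a short wording change in a protocol appendix and one small table from data already collected. The table may hold few cases and will not settle the question of enhancement by itself.
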